2. STUDY DESIGN OBJECTIVES/ENDPOINTS

N: Maximum Number of subjects planned to be enrolled; Mo: Age in Months

*The neurodevelopmental status will be recorded when the subject is 9 months and 18 months of age. It is encouraged that subjects who are getting vaccinated at 18 months of age at Visit 2 or coming for Visit 3, complete their ASQ-3 during their visit to the study centre. In case subjects complete Visit 3 before 18 months of age, the study staff will contact the parents/LAR(s) via phone and conduct an interview to complete the child's ASQ-3 at 18 months of age. For Czech Republic, the phone call at 18 months may be replaced by a clinic visit if deemed preferable by the study team.

** Subjects have received either 2 or 3 doses of Infanrix hexa and Prevnar during the course of the study DTPA (Boostrix)-048, depending on the national/ local routine immunization schedule.

Refer to Section 5.6.2.13 of the protocol for further details.

Pre-Bst: Blood sample to be collected before the booster dose.

Post-Bst: Blood sample to be collected one month after the booster dose.

Protocol waivers or exemptions are not allowed with the exception of immediate safety concerns. Therefore, adherence to the study design requirements, including those specified in the outline of study procedures (Section 5.5 of the protocol), are essential and required for study conduct.

- Experimental design: Phase IV, open-label, non-randomised, multi-centric, multi-country study with two parallel groups.

- Duration of the study: The intended duration of the study, is approximately 9 to 10 months, per subject.
 - Epoch 001: Booster phase starting at Visit 1 (9 months of age) and ending at telephone contact or at Visit 3 (18 or 19 months of age), depending on the time of vaccination. End of Study (EoS): Last testing results released of samples collected at Visit 3.
- Study groups: The study groups and epoch foreseen in the study are presented in [Table 1](#).

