- The verbatim reports of unsolicited AEs will be reviewed by a physician and the signs and symptoms will be coded according to MedDRA. Every verbatim term will be matched with the appropriate Preferred Term. The percentage of subjects with unsolicited AEs occurring within 31-day (Day 0- Day 30) follow-up period after any dose with its exact 95% CI [Clopper, 1934] will be tabulated by group, and by preferred term. Similar tabulation will be done for unsolicited AEs rated as grade 3, for unsolicited AEs with causal relationship to vaccination and AEs/SAEs leading to withdrawal from the study.
- The percentage of subjects who receive concomitant medication and antipyretic medication during the 4-day (Day 0- Day 3) follow-up period and during the entire study period will be tabulated (with exact 95% CI [Clopper, 1934]) after the booster dose.
- Any large injection site reaction (defined as any local swelling with diameter > 50 mm and/or any noticeable diffuse injection site swelling (diameter not measurable) and/or any noticeable increased circumference of the injected limb) reported within 4 days (Day 0-Day 3) following the booster dose will be described in detail.
- Subjects who experience at least one SAE from booster vaccination up to study end will be described in detail.
- Subjects who report at least one SAE after the end of primary study 201330 [DTPA (BOOSTRIX)-048 PRI] and before 201334 [DTPA (BOOSTRIX)-049 BST: 048] study will be described in detail.
- Withdrawal due to AEs and SAEs following vaccinations will be described in detail.
- For the subjects who withdraw from the study after Visit 1 (after completion of ASQ-3 questionnaire but have not received booster vaccination), the analysis will be performed on the Total enrolled cohort.
- Neurodevelopmental status of the subjects will be assessed depending on the ASQ-3 score. The proportion of subjects in the black zone for any domain, for gross motor skills, fine motor skills, communication, problem solving skills and personal-social skills will be tabulated. The proportion of infants referred for formal neurodevelopmental evaluation using BSID-III and those with at least one indicators of neurodevelopmental impairment using BSID-III will also be tabulated.

Handling of missing data:

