- For a given subject and the analysis of solicited AEs, four days post-vaccination (Day 0-Day 3), missing or non-evaluable measurements will not be replaced. Therefore, the analysis of the solicited AEs based on the TVC will include only vaccinated subjects and doses with documented safety data (i.e., symptom screen completed).
- For a given subject, missing neurodevelopmental status will not be replaced. Therefore, an analysis will exclude subjects with missing or non-evaluable measurements

- For analysis of unsolicited AEs, such as SAEs or AEs by primary Medical Dictionary for Regulatory Activities (MedDRA) term, and for the analysis of concomitant medications, all vaccinated subjects will be considered. Subjects, whose parent(s)/LAR(s) do not report the event or the concomitant medication, will be considered as subjects without the event or the concomitant medication, respectively.
- For summaries reporting both solicited and unsolicited AEs, all vaccinated subjects will be considered. Subjects, whose parent(s)/LAR(s) do not report the event or the concomitant medication, will be considered as subjects without the event or the concomitant medication, respectively.

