5.4.2. Additional considerations

- The AEs/SAEs leading to withdrawal from the study will be generated as a listing instead of a table.
- The verbatim reports of unsolicited AEs will be reviewed by a physician and the signs and symptoms will be coded according to MedDRA. Every verbatim term will be matched with the appropriate Preferred Term. The percentage of subjects with unsolicited AEs occurring within 31-day (Day 0- Day 30) follow-up period after the booster dose with its exact 95% CI [Clopper, 1934] will be tabulated by group, and by preferred term.
- Subjects who report at least one SAE after the end of primary study 201330 [DTPA (BOOSTRIX)-048 PRI] and before the booster vaccination in 201334 [DTPA (BOOSTRIX)-049 BST: 048] study will be described in detail.
- The percentage of subjects with congenital anomaly reported across the three studies (047, 048 and 049) with its exact 95% CI [Clopper, 1934] will be tabulated by group, and by preferred term. The details of this analysis are detailed in section 9.
- The neurodevelopmental status of infants will be tabulated at both month 9 and 18.

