Template 29 Percentage of subjects with ASQ-3 score in the black zone for Month 9, 18 (Total enrolled cohort)

Time point	Characteristics	Categories	dTpa Group					Control Group					
			N	n	%	95% CI		N	n	%	95% CI		
						LL	UL				LL	UL	
Month 9	Any domain	Yes											
		No											
	Communication	Yes											
		No											
	Fine motor	Yes											
		No											
	Problem solving	Yes											
		No											
	Personal-Social	Yes											
		No											
Month 18	Any domain	No											
	Communication	Yes											
		No											
	Fine motor	Yes											
		No											
	Problem solving	Yes											
		No											
	Personal-Social	Yes											
	Personal-Social	Yes											
		No											
	Month 9 or 18	Any domain	No										
		Communication	Yes										
			No										
Fine motor		Yes											
		No											
Problem solving		Yes											
		No											
Personal-Social	Yes												

CONFIDENTIAL

201334 [DTPA (BOOSTRIX) -049 BST: 048]
 Statistical Analysis Plan Final

Time point	Characteristics	Categories	dTpa Group					Control Group				
			N	n	%	95% CI		N	n	%	95% CI	
						LL	UL				LL	UL
	Personal-Social	Yes										
	Personal-Social											

dTpa Group = Infants born to mothers belonging to the dTpa Group in study 116945 [DTPA (BOOSTRIX)-047] where mothers received dTpa during pregnancy. All subjects in this group will receive Infanrix hexa co-administered with Prevenar 13 according to the routine national immunisation schedule.

Control Group = Infants born to mothers belonging to the Control group in study 116945 [DTPA (BOOSTRIX)-047] where mothers received placebo during pregnancy. All subjects in this group will receive Infanrix hexa co-administered with Prevenar 13 according to the routine national immunisation schedule.

N = number of subjects enrolled

n = number of subjects in a given category

% = $n / \text{Number of subjects with available results} \times 100$

LL, UL for percentage = Exact 95% Lower and Upper confidence limits

Template 30 Percentage of subjects with confirmed developmental delay as determined by BSID-III at Month 9, 18 (Total enrolled cohort)

Time point	Characteristics	Categories	dTpa Group						Control Group					
			N	n	%	95% CI		N	n	%	95% CI			
						LL	UL				LL	UL		
Month 9	Any domain	Yes												
		No												
		Missing												
	Cognitive	Yes												
		No												
		Missing												
	Language	Yes												
		No												
		Missing												

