Group	Timing	N	ASQ-3 score in the black zone for at least one domain		At least one of the indicators of neurodevelopmental delay using BSID III among the infants referred for BSID III evaluation		Estimated proportion of infants with at least one of the indicators of neurodevelopmental delay using BSID-III				
			n/N	%	n'/N'	%	n/N x n'/N'	%	LL	UL	
DTPa group	Month 9										
	Month 18										
	Month 9 or 18										
Control group	Month 9										
	Month 18										
	Month 9 or 18										

N = number of subjects enrolled

n/N = number of subjects with ASQ-3 below cut off / number of enrolled subjects

n'/N' = number of subjects with at least one indicator of neurodevelopmental delay using BSID III / number of subjects referred for BSID III evaluation

% = proportion of subjects with neurodevelopmental impairment at x time point

n/N x n'/N' = the multiplication of the two proportions

95% CI = exact 95% confidence interval (Clopper Pearson or Greenwood formula); LL = lower limit, UL = upper limit

Template 32 Evolution graph for the pertussis antibodies (Adapted ATP cohort)

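### The combined Month 9 or 18 ASQ-3 row has an undefined denominator in Template 29 and a conflicting all-enrolled denominator in Template 31, which counts a missing 18-month result as negative

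*SAP*

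**What the plan says.** Template 29, titled "Percentage of subjects with ASQ-3 score in the black zone for Month 9, 18 (Total enrolled cohort", tabulates black-zone scores for Month 9, Month 18, and Month 9 or 18 combined. Its footnote gives "N = number of subjects enrolled" for the N column but takes percentages over "Number of subjects with available results". It does not say what makes a result available in a row that spans two assessments.

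Template 31 also has a Month 9 or 18 row. Its footnote is explicit: "n/N = number of subjects with ASQ-3 below cut off / number of enrolled subjects". That proportion is then multiplied by the BSID-III proportion to give the estimated impairment rate.

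Two statements in SAP 5.4.1 bear on the denominator. The missing-data rule reads: "For a given subject, missing neurodevelopmental status will not be replaced. Therefore, an analysis will exclude subjects with missing or non-evaluable measurements". For infants who leave after Visit 1 with a completed ASQ-3 but no booster, "the analysis will be performed on the Total enrolled cohort".

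On timing, SAP section 2 says: "In case subjects complete Visit 3 before 18 months of age, the study staff will contact the parents/LAR(s) via phone". The 18-month ASQ-3 can therefore be missed by an infant who attended Visit 3. SAP 5.4.2 says: "The neurodevelopmental status of infants will be tabulated at both month 9 and 18". The combined row appears only in the mock tables.

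**The concern.** An infant in the black zone at 9 months is positive for the combined row whatever happens later. An infant not in the black zone at 9 months is known to be negative only once the 18-month result is in. If such an infant has no 18-month ASQ-3 but stays in the denominator, one of two assessments is silently scored as negative. The error runs one way, downward, and grows with 18-month loss.

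Template 31's footnote does exactly this, and also scores a missing 9-month result as negative. Template 29 does it if one result is enough to count as available.

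At stake is the descriptive cumulative proportion in each group, its confidence interval, and the Template 31 impairment estimate built on it. If the two groups differ in 18-month completeness, part of any observed difference would reflect that.

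**Working it through.** The documents state no ASQ-3 rate and no 18-month completeness, so there is no plan figure to reproduce. Every rate below is an assumption.

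**Inputs**
- p9 = proportion positive at 9 months; q = proportion newly positive at 18 months among those negative at 9 months. Assumed pairs (p9, q): (5%, 4%), (10%, 7%), (15%, 10%).
- m = share with no 18-month ASQ-3. Assumed 20% and 40%. Protocol 10.3 expects a 20-40% loss of evaluable subjects. That figure is not about ASQ-3 completion and only sets the range.
- Every infant has a 9-month result, and loss is at first unrelated to outcome.
- Group size 340, the protocol maximum.

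**Formulas**
- True cumulative rate: T = p9 + (1 - p9)q
- Any-result denominator (equal to Template 31's all-enrolled denominator when all 9-month results are present): A = p9 + (1 - p9)q(1 - m)
- Infants with both results: B = T when loss is unrelated to outcome
- Positive on either result, negative only with both: D = A / [A + (1 - p9)(1 - q)(1 - m)]

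**Worked case, p9 = 10%, q = 7%**
- T = 0.10 + 0.90 x 0.07 = 16.3%
- A at m = 20%: 0.10 + 0.063 x 0.8 = 15.0%; at m = 40%: 0.10 + 0.063 x 0.6 = 13.8%
- D at m = 20%: 0.1504 / (0.1504 + 0.6696) = 18.3%; at m = 40%: 0.1378 / (0.1378 + 0.5022) = 21.5%

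| p9, q | T | A, m = 20% | A, m = 40% | Shift (T - A) |
|---|---|---|---|---|
| 5%, 4% | 8.8% | 8.0% | 7.3% | 0.8 to 1.5 points |
| 10%, 7% | 16.3% | 15.0% | 13.8% | 1.3 to 2.5 points |
| 15%, 10% | 23.5% | 21.8% | 20.1% | 1.7 to 3.4 points |

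**Between groups.** With identical development (10%, 7%) and 10% versus 30% missing, the false gap under A is 0.90 x 0.07 x (0.30 - 0.10) = 1.26 points.

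**Carry-over into Template 31.** For a fixed BSID-III proportion, the impairment estimate is scaled by A/T: 15.04/16.3 = 0.92 at 20% missing and 13.78/16.3 = 0.85 at 40%.

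**When loss depends on the 9-month result.** Black-zone infants are referred to a specialist, so their retention may differ from that of other infants. Keep T = 16.3%.
- 18-month completeness 90% in 9-month positives, 70% in negatives: B = (0.10 x 0.9 + 0.90 x 0.07 x 0.7) / (0.10 x 0.9 + 0.90 x 0.7) = 0.1341/0.72 = 18.6%
- Reversed, 70% and 90%: B = (0.07 + 0.0567) / (0.07 + 0.81) = 14.4%
- p9 + (1 - p9) x P(positive at 18 | negative at 9) gives 16.3% in both cases, because each factor is estimated within its own observed set.

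**The case against.** The strongest reply is that Template 29 does not prescribe the any-result rule. Its footnote leaves the term undefined, and the 5.4.1 exclusion of missing measurements can be read as requiring both results. Under loss unrelated to outcome, that version returns exactly 16.3%. This stands: for Template 29 the defect is an undefined denominator, not a rule shown to be biased. The 5.4.1 sentence keeping early leavers in the Total enrolled cohort lends the any-result reading support but does not settle it, because that sentence concerns the cohort and not the percentage denominator. The reply does not help Template 31, whose denominator is explicit.

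A reader might infer that the percentage tracks completeness instead of development. It tracks both. With 15% versus 10% positive at each age, independent between ages, the any-result gap is 8.7 points at full completeness, 8.0 at 80% and 7.2 at 60%.

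A reader might also take the combined row as the headline of the neurodevelopment objective, or expect a false group difference. The endpoints name 9 and 18 months, and the combined row is only in mock tables that Annex 3 calls illustrative and open to adaptation. A false difference needs unequal completeness, and nothing in the documents predicts that: both groups follow the same procedures. All analyses are descriptive, and the shift lies within sampling error; the exact 95% interval for 55/340 (16.2%) is 12.4 to 20.5.

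The illustrative status does not remove the need for a decision. These footnotes are the only denominator rules given for the combined row, and they disagree.

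**Conclusion.** The point holds as a conflict between the two templates, with a one-directional consequence. Template 31's all-enrolled rule, and Template 29's rule if one result suffices, understate the cumulative black-zone proportion whenever 18-month results are missing in infants negative at 9 months. The understatement is roughly 1 to 3 points at 20-40% missing under the assumed rates, and Template 31 carries it into the impairment estimate.

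The size rests wholly on assumed positivity and completeness. The Month 9 and Month 18 rows of Template 29 are untouched by this mechanism. No test or decision rule depends on the combined row, but it bears on a secondary objective and can be settled before analysis at almost no cost.

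**What to change.** Estimate the Month 9 or 18 row in both templates as p9 + (1 - p9) x P(positive at 18 | negative at 9). Take p9 from all infants with a 9-month result and the second factor from 9-month-negative infants with an 18-month result. Show both denominators and use a Greenwood-type interval, which SAP 9.2 already adopts for missing BSID-III results. This needs only that, given the 9-month result, loss is unrelated to the 18-month result.

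A simpler alternative is to use infants with both results as the denominator, with the any-result version as a sensitivity analysis. The SAP should then say that this is unbiased only if loss is unrelated to the 9-month result.

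Either way, replace the enrolled-subjects denominator in Template 31's combined row with the same quantity, and report 18-month ASQ-3 completeness by group.

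The cost is a short SAP addition, a few lines of code and a slightly wider interval. At p9 = 10%, q = 7%, 340 infants and 20% missing, the variance is 0.837² x [0.10/(340 x 0.90) + 0.07/(340 x 0.90 x 0.8 x 0.93)]. The half-width is 1.96 times its square root, 4.1 points. With complete data it is 1.96 x √(0.163 x 0.837/340) = 3.9 points.

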#### **5.6.2.13. Assessment of neurodevelopmental status**

The parent(s)/LAR(s) will be asked to complete a standardised developmental screening tool known as ASQ-3 when the subject is 9 months and 18 months old [ASQ-3, 2016]. The ASQ-3 has been used globally and translated into different languages. The tool has been demonstrated to reliably and accurately identify children with delays who should receive further in-depth assessment. The ASQ-3 includes a series of questions designed to assess five areas of development: communication, gross motor, fine motor, problem solving, and personal-social. The questions target behaviours that are appropriate for particular developmental status. These behaviours are easy for the parent(s)/LAR(s) to observe and they are asked to indicate whether or not the subject can perform the behaviour. The ASQ-3 will be completed by the *investigator or designee with* the parent(s)/LAR(s) *during the study visits or phone call* when the subject is 9 and 18 months of age, via a paper questionnaire \*. These time- points comply with the recommended developmental screening assessment guidelines from the American Academy of Pediatrics [Council on Children with Disabilities, 2006]. *The investigator or designee may discuss the results with the parents if deemed necessary. (Amended 12 December 2016)*

The ASQ-3 has narrow age intervals (*9 months and 0 days through 9 months and 30 days and 17 months and 0 days through 18 months of age and 30 days*), so age must be calculated to the month and day from the date the ASQ-3 will be completed. **(Amended 12 December 2016)**

If a baby was born three or more weeks prematurely, the number of weeks premature should be subtracted from the child's actual age [ASQ, 2014]. Refer to the SPM for more details and examples.

Any subject who scores below the cut-off i.e., a score more than 2 Standard Deviations (SDs) below the mean score for the U.S. reference group (i.e., black zone in the score chart) in any of the five domains of the ASQ-3 (i.e., communication, gross motor, fine motor, problem solving, and personal-social) will be referred to a developmental specialist for formal neurodevelopmental assessment (e.g., using the Bayley Scale for Infant Development, Version III [BSID-III]) [Bayley-III, 2006]. An overall neurodevelopmental assessment in the areas of cognitive, language, motor, social-emotional and adaptive behaviour will be rendered using BSID-III. A BSID-III score

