9.2. Statistical Method

If all subjects with ASQ-3 score in the black zone for at least one domain have BSID-III results, the clopper and Pearson CI will be used for the % of subjects with neurodevelopmental impairment.

If some subjects with ASQ-3 score in the black zone for at least one domain have no BSID-III results, the Greenwood formula [S.Sawyer,2003] for censored BSID-III data

will be used to estimate the % of subjects with neurodevelopmental impairment and associated CI.

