	Motor	Yes												
		No												
		Missing												
	Emotional	Yes												
		No												
		Missing												
Behaviour	Yes													
	No													
	Missing													
Month 18	Any domain	Yes												
		No												
		Missing												
	Cognitive	Yes												
		No												
		Missing												
	Language	Yes												
		No												
		Missing												
	Motor	Yes												
		No												
		Missing												
	Emotional	Yes												
		No												
		Missing												
Behaviour	Yes													
	No													
	Missing													
Month 9 or 18	Any domain	Yes												
		No												
		Missing												
	Cognitive	Yes												
		No												
		Missing												
	Language	Yes												
		No												
		Missing												
	Motor	Yes												
		No												
		Missing												

CONFIDENTIAL

201334 [DTPA (BOOSTRIX) -049 BST: 048]
Statistical Analysis Plan Final

Time point	Characteristics	Categories	dTpa Group					Control Group				
			N	n	%	95% CI		N	n	%	95% CI	
						LL	UL				LL	UL
	Emotional	Yes										
		No										
		Missing										
	Behaviour	Yes										
		No										
		Missing										

dTpa Group = Infants born to mothers belonging to the dTpa Group in study 116945 [DTPA (BOOSTRIX)-047] where mothers received dTpa during pregnancy. All subjects in this group will receive Infanrix hexa co-administered with Prevenar 13 according to the routine national immunisation schedule.

Control Group = Infants born to mothers belonging to the Control group in study 116945 [DTPA (BOOSTRIX)-047] where mothers received placebo during pregnancy. All subjects in this group will receive Infanrix hexa co-administered with Prevenar 13 according to the routine national immunisation schedule.

N = number of subjects enrolled

n = number of subjects in a given category

% = $n / \text{Number of subjects with available results} \times 100$

LL, UL for percentage = Exact 95% Lower and Upper confidence limits

Missing: number of subjects with ASQ-3 score in the black zone which are not referred for the BSID III

Template 31 Proportion of subjects with neurodevelopmental delay (Total enrolled cohort)

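### Template 30 counts missing BSID-III data by non-referral, SAP 9.2 by absence of a result, so loss after referral goes unreported as missing

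*SAP*

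**What the plan says.** **Referral (Protocol 5.6.2.13).** The rule covers "Any subject who scores below the cut-off i.e., a score more than 2 Standard Deviations (SDs) below the mean score" in any of the five ASQ-3 domains. Such an infant "will be referred to a developmental specialist for formal neurodevelopmental assessment (e.g., using the Bayley Scale for Infant Development, Version III"; BSID-III is therefore given as an example of the instrument. The same section has two items entered in the eCRF: the fact of referral and the specialist's overall assessment of delay.

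**Method (SAP 9.2).** If every black-zone infant has a BSID-III result, a Clopper-Pearson interval is used. The alternative opens with "If some subjects with ASQ-3 score in the black zone for at least one domain have no BSID-III results", and then the Greenwood formula for censored data applies. The test is whether a result exists.

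**Template 30 (SAP Annex 3).** It has *Yes*, *No* and *Missing* rows for any domain and for each BSID-III domain, at Month 9, Month 18 and either time. N is the number enrolled, and the percentage is taken over the "Number of subjects with available results". The only definition of the third row is "Missing: number of subjects with ASQ-3 score in the black zone which are not referred for the BSID III". *Yes* and *No* are not defined.

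**Template 31 (SAP Annex 3).** The denominator N' of the second proportion is the "number of subjects referred for BSID III evaluation".

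**The concern.** Referral and result are different facts, and the plan treats them so elsewhere: the proportion referred and the proportion with an impairment indicator are separate secondary endpoints (Protocol 10.2, SAP 3.4). The loss to be expected lies between the two steps: a family does not attend or declines, or the result never reaches the eCRF. A row defined by non-referral does not count that loss.

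At stake is the reported completeness of verification. Protocol 1.2.2 gives the unknown effect of maternal vaccination on neurodevelopment as the reason for this assessment. A reader needs to know how many screen-positive infants were never formally assessed. Template 30 could report none missing while Template 31 applies a censored-data formula because of those same infants. The referral-based wording recurs in N' of Template 31, where it can change a printed proportion.

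**Working it through.** The documents state no figure on this point, so there is none to reproduce. The check is a count of rows, then an illustration.

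**Step 1. Where a black-zone infant goes.** *Yes* and *No* are read here as BSID-III results with and without impairment.

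| Black-zone infant | Template 30 footnote | SAP 9.2 |
|---|---|---|
| Referred, result available | *Yes* or *No* | has a result |
| Referred for BSID-III, no result | not *Missing* | no result |
| Not referred for BSID-III, no result | *Missing* | no result |

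The definitions part in the middle line, which is the only line of loss if the protocol's referral rule is met and the referral is for BSID-III.

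**Step 2. Size of the gap.** Let B be the black-zone count, R the number referred for BSID-III and A the number with a result.

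- *Missing* by footnote = B − R
- *Missing* by SAP 9.2 = B − A
- Gap = R − A. With R = B the footnote gives 0 and the gap is B − A.

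Inputs: 340 per group is the planned maximum (Protocol, Table 1). Black-zone shares of 5, 10 and 20% and losses after referral of 0 to 50% are assumptions. Infants per group not counted as *Missing*, with R = B, in whole infants (8.5 taken as 8):

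| Black zone of 340 | 0% lost | 10% | 30% | 50% |
|---|---|---|---|---|
| 17 (5%) | 0 | 2 | 5 | 8 |
| 34 (10%) | 0 | 3 | 10 | 17 |
| 68 (20%) | 0 | 7 | 20 | 34 |

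The footnote row is 0 in every cell.

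**Step 3. What an undefined *No* can do.** Take B = 34, 10 lost, A = 24 and 7 impaired (about 30% of those assessed, also assumed).

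- The 10 are dropped: 7/24 = 29.2% in Template 30, with *Yes* + *No* + *Missing* = 7 + 17 + 0 = 24, not 34.
- The 10 are counted as *No*: 7/34 = 20.6%, and missing data have become negative findings.

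The percentage base of available results favours the first reading but does not settle it.

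**Step 4. The same wording in Template 31.** The estimate is n/N × n'/N'.

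- N' = referred (34): 34/340 × 7/34 = 7/340 = 2.06%
- N' = with a result (24): 34/340 × 7/24 = 2.92%
- With 17 lost and 5 of 17 impaired: 5/340 = 1.47% against 34/340 × 5/17 = 2.94%

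Under full referral, N' = referred reduces the product to n'/N and treats every unassessed infant as unimpaired. That does not fit a method meant for censored results.

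**Step 5. After the change.** With *Missing* defined by result, the example prints 10, and 7 + 17 + 10 = 34.

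**The case against.** The strongest reply is that Annex 3 calls its displays and footnotes illustrative and open to adaptation, says they were copied from recent studies, and allows minor changes without a SAP amendment. Unadapted text is easy to find: Template 15 lists other vaccines, and Template 25 an age band of 6 to 14 weeks. The controlling list of tables is held elsewhere (SAP 10.2). This lowers the weight of the point. It does not remove it: the annex also says that these mocks are to be used, and this footnote names ASQ-3, the black zone and BSID-III. It is the only definition of the row.

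The second reply is that SAP 9.2 already covers black-zone infants without a result, whatever the reason. That stands. A reader might infer that the *Missing* row decides which estimator is used. It does not: the data trigger the choice, and no estimate is computed from this row. The shortfall could also be recovered by setting Template 31's black-zone count against *Yes* and *No* in Template 30, if those rows mean results.

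A reader might also infer that Template 30 can never show missing data, however great the loss. The documents do not support that. A black-zone infant whom the site fails to refer would appear in the row. So might one sent to a specialist who uses another tool, since BSID-III is only an example in the protocol.

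Nor do the documents say that referred infants without a result fall in no row. With *No* undefined, that is one of two readings.

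**Conclusion.** The inconsistency is real and minor. Template 30 defines missing BSID-III data by non-referral and SAP 9.2 by absence of a result. Where black-zone infants are referred for BSID-III as the protocol directs, those without a result are not counted as *Missing*, and the row understates the loss, to 0 under full referral. Whether they are then dropped or counted as *No* cannot be told from the plan.

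The effect is on the reported completeness of a secondary safety endpoint, in a mock table described as adaptable. The number affected depends on black-zone and completion rates that the documents do not give; the assumed range in the working runs from 0 to 34 infants per group. The differences in the estimated proportion (2.06% against 2.92%, 1.47% against 2.94%) arise from N' in Template 31, not from the Template 30 row, and rest on the same assumptions.

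**What to change.** In Template 30:

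- For *Any domain*, define *Missing* as black-zone infants with no BSID-III result, split into not referred and referred without a BSID-III result. The second part includes infants assessed with another instrument.
- Define *No* as a BSID-III result without impairment.
- Require *Yes* + *No* + *Missing* to equal the black-zone count at that time point.
- Apply this to single BSID-III domains only where domain-level results are captured.

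In Template 31, set N' to infants with a BSID-III result, as SAP 9.2 implies.

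The cost is a few footnotes and one extra row, and Annex 3 lets minor changes to the mocks be made without a SAP amendment. Referral status is already entered in the eCRF. Protocol 5.6.2.13 otherwise mentions only the overall assessment, so it should first be confirmed that the eCRF shows whether a result came from BSID-III and whether it holds domain results. If it does not, the per-domain rows would need data that the documents do not show to be collected.
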